9.5. Study Drug Dose Adjustment and Stopping Rules

Starting on Day 8 (Visit 3), attempts should be made to achieve and maintain the target dose of ALKS 5461 2/2 over the course of treatment, if tolerated. However, at any time during the study, flexible down-titration to ALKS 5461 1/1 and then to ALKS 5461 0.5/0.5 is permitted at the investigator's discretion, if tolerability issues persist. Once a subject has stabilized after down-titration, attempts should again be made to achieve and maintain the target dose of ALKS 5461 2/2 over the course of treatment, dependent on the individual subject's experience with study drug tolerability.

Dose adjustment of approved ADT during the treatment period is permitted for optimal therapeutic effect within the recommended approved dose range, however ADT dose adjustment should not be made within the same week as ALKS 5461 dose adjustment. Furthermore, subjects are not permitted to change ADTs during the course of the study period.

The study may be stopped at any time or study sites may be closed at the sponsor's discretion.

10. STUDY DRUG MATERIALS AND MANAGEMENT

10.1. Packaging and Labeling

A subset of subjects in North America may receive ALKS 5461 in child-resistant bottles. Otherwise, study drug will be packaged in child-resistant blister packs. All packaging will be labeled in a manner that meets applicable local and regulatory requirements.

Dosing for Week 1 will be in accordance with [Table 1](#). During this period subjects will receive either child-resistant bottles or child-resistant blister packs containing 9 tablets to cover the week from Visit 2 to Visit 3 (+2 day visit window). During Week 1, titration packaging will be either blinded or unblinded dependent on the antecedent study, as outlined in [Table 1](#).

All subjects will receive open-label child-resistant bottles or open-label child-resistant blister packs of ALKS 5461 on Visit 3 through Visit 13, each containing 9 tablets. The number of bottles or blister packs distributed to the subject at each visit will be dependent upon the number of days between the specific scheduled visits.

Subjects should follow the dosing instructions as printed on the packaging.

10.2. Storage

ALKS 5461 contains BUP and samidorphan. Under the US Controlled Substances Act, buprenorphine is a Schedule III narcotic. Samidorphan is considered a Schedule II controlled substance, derived from opium alkaloids. Therefore, ALKS 5461 must be stored in accordance with local controlled substance requirements, and in the US, restrictions related to Schedule II controlled substances.

The investigator will take adequate precautions, including storage of the investigational drug in a securely locked, substantially constructed cabinet, or other securely locked, substantially constructed enclosure, access to which is limited, to prevent theft or diversion of the substance into illegal channels of distribution.

Complete details on storage condition requirements can be found in the [Investigator's Brochure](#).

10.3. Accountability

The investigator will be responsible for the oversight of recording the receipt and administration of ALKS 5461, and for insuring the supervision of the storage and allocation of these supplies.

The investigator is required to maintain current drug dispensing and accountability logs throughout the study. The investigator may delegate accountability duties to an appropriate and qualified pharmacist or staff member who is under the supervision of the investigator.

The investigator or designee must allow the Clinical Research Associate or equivalent to perform drug reconciliation during each study monitoring visit. All unused supplies will be checked against the study drug movement records before investigational drug is returned or destroyed.

Subject-level study drug accountability will be documented in the subjects' source documents and eCRFs. If drug cannot be accounted for, actions will be taken that are appropriate for a drug

containing controlled substances. These actions may include but are not limited to re-training subject on adherence or discontinuation of subject from the trial.

10.4. Handling and Disposal

All unused study drug, which contains the controlled substances buprenorphine and samidorphan, must be handled and disposed of in accordance with the Good Clinical Practice (GCP), Good Manufacturing Practice (GMP), and controlled substance requirements. The sponsor will provide additional instruction as to the disposition of unused investigational product. Until instructions have been provided, each study site must store unused materials on site in the manner described in [Section 10.2](#). All study drug must be accounted for on the study drug accountability logs.

11. ASSESSMENT OF EFFICACY

ALKS 5461 treatment effect over time will be assessed in an exploratory manner based on change from baseline in MADRS total score, HAM-A score, and CGI-S score.

12. ASSESSMENT OF PHARMACOKINETICS

Concentrations of BUP, samidorphan, their relevant metabolites, and reported background ADTs will be quantified in consenting subjects enrolled in the US only. Plasma samples will be collected at time points shown in [Table 2](#).

13. ASSESSMENT OF SAFETY

Safety and tolerability will be assessed on the basis of:

- treatment-emergent AEs (TEAEs)
- clinical laboratory parameters (ie, hematology, chemistry, and urinalysis)
- vital sign measurements (ie, oral body temperature, respiratory rate, blood pressure, and pulse)
- weight
- ECG findings
- C-SSRS results
- COWS

13.1. Definition of Adverse Event

An AE is any untoward medical occurrence in a patient or clinical investigation subject administered a pharmaceutical product. The occurrence, which may or may not have a causal relationship with the investigational treatment, may include any clinical or laboratory change that does not commonly occur in that subject and is considered clinically significant.

Illnesses present prior to the subject signing the informed consent form (ICF) are considered to be pre-existing conditions (which may include AEs from a previous ALKS 5461 study for Continuing Subjects or Lead-in Subjects) and are documented on the medical history eCRF. Pre-existing conditions that worsen during the study are entered on the AE eCRF.

All out-of-range laboratory values will be deemed as clinically significant or not clinically significant by the investigator. Clinically significant values will be considered AEs and recorded as such on the eCRFs.

Pregnancy is not considered an AE, although a subject will be withdrawn from the study if a pregnancy occurs. As described in [Section 8.4.1](#), the pregnancy must be reported to Alkermes and additional follow-up may be required.

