13.4. Monitoring and Recording of Adverse Events

AE data collection will begin after a subject signs the ICF and will continue until completion of the final safety follow-up visit. Any AE or SAE having an onset after the final safety follow-up visit will not be collected or reported unless the investigator feels that the event may be related to the study drug.

Subjects will be instructed by the investigator or designee to report the occurrence of any AE. All volunteered, elicited, and observed AEs are to be recorded on the AE eCRFs.

The investigator will assess all AEs regarding any causal relationship to the study drug (see Section 13.3), the intensity (severity) of the event, action taken, and subject outcome.

The following criteria should be used to guide the assessment of intensity (severity):

- **Mild:** Causes awareness of sign or symptom, but is easily tolerated; does not interfere with usual activities
- **Moderate:** Causes discomfort enough to interfere with usual activities
- **Severe:** Is incapacitating; results in inability to work or perform usual activities

All AEs will be followed until resolution, until deemed stable by the investigator, or until the subject is deemed by the investigator to be lost to follow-up.

For clinical study safety reporting purposes, the most recent version of the IB will be used as the reference document to designate event expectedness.

Withdrawal from the study as a result of an AE and any therapeutic measures that are taken shall be at the discretion of the investigator. If a subject withdraws from the study for any reason, any ongoing AEs will be followed until resolution, until deemed stable by the investigator, or until the subject is deemed by the investigator to be lost to follow-up.

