3. DATA ANALYSIS

3.1. General Statistical Methodology

The safety and efficacy endpoints will be summarized by prior ALKS 5461 exposure: no prior exposure to ALKS 5461 and prior exposure to ALKS 5461, as well as overall.

Subjects with no prior exposure to ALKS 5461 come from three sources: De Novo (i.e., New Subjects), PLI Failures (i.e., antecedent study Prospective Lead-in Subjects Failures) and Placebo (i.e., those who did not receive any active treatment in an antecedent study).

Prior exposure to ALKS 5461 subjects include Continuing Subjects who received active treatment (doses ALKS 5461 0.5/0.5, ALKS 5461 1/1, or ALKS 5461 2/2) in an antecedent study. Subjects with prior exposure are designated as such independent of the duration of exposure in the antecedent trial.

In general, summary statistics (n, mean, standard deviation [SD], median, minimum, and maximum for continuous variables, and number and percentage of subjects in each category for categorical variables) based on observed data will be provided by prior ALKS 5461 exposure and overall. Measurements collected from unscheduled visits or repeated assessments will not be included in the by-visit summary tables or figures, but will be included in categorical outlier analyses of post-baseline values and subject listings.

In general, only data collected during the ALK5461-208 study will be summarized even though the baseline may come from an antecedent study.

Last assessment during treatment period, defined as the last non-missing value from scheduled post-baseline visit during the treatment period (i.e., from Visit 2 to Visit 14, inclusive), will be included in the by-visit summary tables for both efficacy and safety endpoints as appropriate.

Source data for the summary tables will be presented as subject data listings. Please refer to Section 6.1 on the handling of data collected at an early termination visit.

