3.3. Demographics and Baseline Characteristics

For New Subjects only, demographic and baseline characteristics data (including MDD history) will be collected at screening visit. For Continuing Subjects and Lead-in Subjects, these data will be carried over from information recorded in the antecedent ALKS 5461 study in which they participated.

Demographics and baseline characteristics (age, gender, primary race, ethnicity, region (United States [US], non-US), duration of current MDE, ADT Class for current MDE, number of inadequate responses to ADT in the current MDE, lifetime number of MDEs, lifetime number of antidepressants, benzodiazepines (BDZ) use, opioid use, H1 antagonist use, height, weight, body mass index [BMI]) will be summarized by prior exposure to ALKS 5461, no prior exposure to ALKS 5461, and overall for the Safety Population. For no prior exposure to ALKS 5461, the group is divided further into 3 subgroups of De Novo, PLI Failures, and Placebo, as well as overall. Categories for missing data will be provided as necessary.

Baseline characteristics for efficacy measurments (MADRS-10 score, MADRS-6 score, HAM-A total score, CGI-S score and HAM-D total score) will be summarized by prior exposure to ALKS 5461, no prior exposure to ALKS 5461, and overall for the FAS Population. For no prior exposure to ALKS 5461, the group is divided further into three subgroups of De Novo, PLI Failures, and Placebo, as well as overall. The baseline for efficacy measurements is defined as the last non-missing value on or before the date of initiation of ALKS 5461 at any dose.

Medical and psychiatric history will be summarized using the number of observations and percentage of subjects reporting each category by prior ALKS 5461 exposure and overall for the Safety Population.

Demographic and baseline listings will be provided for all subjects.

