3.7.2. Adverse Events

Adverse events will be coded by System Organ Class and Preferred Term using the Medical Dictionary for Regulatory Activities MedDRA version 19.0. The verbatim term will be included in the AE listings. An AE will be considered as a treatment emergent adverse event (TEAE) if it starts or worsens (if present at baseline) on or after the baseline during treatment period. An AE will be considered as a PDEAE if it starts or worsens during the Post-discontinuation Safety Period which is after the last dose date plus 1 day. For the determination of TEAEs during the treatment period, AEs with the greatest severity before the baseline will be used as the benchmark for the comparison of the AEs occurring during the treatment period. For PDEAEs, the greatest severity before or on the last dose date plus 1 day will be used as the benchmark for the comparison of the AEs occurring during the Post-discontinuation Safety Period.

All AEs will be listed by subject. TEAEs / PDEAEs, deaths, serious adverse events (SAEs), AEs leading to study discontinuation will be included in the summary tables. Summary tables will be provided by prior ALKS 5461 exposure and overall for the Safety Population. For AEs leading to study discontinuation or deaths, the AEs will be summarized in the period in which the discontinuation or death occurred. Drug related TEAEs include those scored as definitely related, probably related, and possibly related by the investigator.

The following summary tables will be produced for the treatment period / Post-discontinuation Safety Period by prior ALKS 5461 exposure and overall for the Safety Population:

- Overview AE summary tables (TEAEs / PDEAEs)
- TEAEs / PDEAEs by System Organ Class and Preferred Term
- TEAEs / PDEAEs by Preferred Term in decreasing frequency
- TEAEs / PDEAEs experienced by ≥5% of subjects (in any group) by Preferred Term
- TEAEs / PDEAEs by System Organ Class, Preferred Term, and Severity
- Drug-related TEAEs by System Organ Class and Preferred Term
- SAEs (fatal and non-fatal) by System Organ Class and Preferred Term
- SAEs (fatal and non-fatal) by Preferred Term in decreasing frequency
- AEs leading to study discontinuation by System Organ Class and Preferred Term
- AEs leading to study discontinuation by Preferred Term in decreasing frequency
- TEAEs by System Organ Class, Preferred Term, and Duration of Exposure
- TEAEs by Preferred Term in decreasing frequency and Duration of Exposure

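### AEs that began on ALKS 5461 in an antecedent study and continue unchanged into study 208 are filed as medical history, so they miss the 208 TEAE, PDEAE, AESI and TEAE-duration tables and appear unmarked among pre-drug conditions

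*Protocol*

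**What the plan says.** Protocol 13.1 sets the recording rule. "Illnesses present prior to the subject signing the informed consent form (ICF) are considered to be pre-existing conditions", and the text adds of these conditions: "which may include AEs from a previous ALKS 5461 study for Continuing Subjects or Lead-in Subjects) and are documented on the medical history eCRF". The general way back to the AE form comes next: "Pre-existing conditions that worsen during the study are entered on the AE eCRF". For laboratory results outside the reference range the same section has a separate sentence with no condition of worsening: "Clinically significant values will be considered AEs and recorded as such on the eCRFs". Protocol 13.4 fixes the starting point: "AE data collection will begin after a subject signs the ICF".

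SAP 3.1 then limits the data: "In general, only data collected during the ALK5461-208 study will be summarized even though the baseline may come from an antecedent study". It states no exception for AEs. For rollover subjects, SAP 3.2.1 (Table 2) and 3.7.2 count a TEAE only if it arises or gets worse after Visit 2. SAP 3.7.3 builds the AESI summaries from TEAEs and PDEAEs. On history, SAP 3.3 says: "Medical and psychiatric history will be summarized using the number of observations and percentage of subjects reporting each category by prior ALKS 5461 exposure". It has no category for onset on study drug.

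Discontinuations come from two sources. SAP 3.2.2 takes the reasons, and the Kaplan-Meier analysis of stopping due to an AE, from the disposition CRF. SAP 3.7.2 plans tables of "AEs leading to study discontinuation by System Organ Class and Preferred Term", which need an AE record.

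**The concern.** The only objective of the study is long-term safety and tolerability. For a Lead-in Subject, or a Continuing Subject who had placebo, filing an ongoing complaint as history is correct, because no ALKS 5461 had been taken. For a Continuing Subject who had ALKS 5461, the complaint began on the drug under study, and the subject goes on taking that drug. A persistent effect is what a long-term study should describe, yet an unchanged one is shown as background illness.

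The SAP presents its AE tables by prior exposure. The omission therefore lowers the prior-exposure column only and can make it look better tolerated than it was. It also costs information: Protocol 13.4 requires relationship, severity, action taken and outcome for AEs, and the documents ask for none of these for a history entry.

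**Working it through.** No plan figure exists to reproduce, so the check follows one case through the rules. Take a Continuing Subject from ALK5461-206 who developed somnolence on ALKS 5461 (a listed AESI term, SAP Appendix 6), has it at the same severity at Visit 2, and keeps it unchanged.

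| Output | Governing rule | Result |
|---|---|---|
| AE form | Protocol 13.1: present before consent, not worse | No entry |
| TEAE tables | SAP 3.2.1, 3.7.2: new or worse after Visit 2 | Not counted |
| PDEAE tables | SAP 3.7.2: new or worse once the last dose date plus 1 day has passed | Not counted |
| AESI summaries | SAP 3.7.3: TEAEs or PDEAEs | Not counted |
| TEAE-duration table | SAP 3.7.2: TEAEs only | Not counted, even if it lasts all 52 weeks |
| Medical-history table | SAP 3.3 | Counted, with no mark of onset on drug |
| Disposition reasons and Kaplan-Meier | SAP 3.2.2: disposition CRF | Counted if AE is given as the reason for stopping |
| Discontinuation tables by SOC and preferred term | SAP 3.7.2: AEs, not limited to TEAEs | Needs an AE record, which 13.1 does not provide |

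The last two rows can disagree for the same subject, and the SAP has no reconciliation step.

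**Who is affected.** Actively treated Continuing Subjects. Under Protocol Table 1, those from 206, 207 and 210 enter on drug. Those from 205 enter after a 1-week discontinuation, so only an event that outlasts that week is carried over; one that resolves and returns is a new onset. Laboratory findings judged clinically significant become AEs in any case, so the gap mainly concerns symptoms.

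**Three related points.**
- For the same subjects, SAP 3.2.1 takes the efficacy baseline from before the first ALKS 5461 dose in the antecedent study, while the AE baseline is Visit 2. Benefit gained earlier is credited to the drug; harm carried over becomes history.
- SAP 3.7.2 judges worsening against the greatest severity before baseline. For rollover subjects, Table 2 names no source for that value.
- Protocol 8.3.4 carries medical history over from the antecedent record. It is unclear how an AE that arose during that study reaches the 208 history form.

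**Size, algebra only.** Let p be the share of prior-exposure subjects who enter with a given term ongoing and keep it unchanged, and q the new-onset rate in the rest, with everyone in the denominator.

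- Reported TEAE incidence: q(1 − p)
- Incidence present on drug: q(1 − p) + p
- Shortfall: p

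With assumed values q = 5% and p = 5%: reported 0.05 × 0.95 = 4.75%; present 4.75% + 5% = 9.75%. With p = 1%: 4.95% and 5.95%. With p = 10%: 4.50% and 14.50%. Neither q nor p is in the documents. The example shows that a term present in well over 5% of the group can fall below the 5% cut-off that SAP 3.7.2 uses for its common-TEAE table; it would still be listed there if the other group reached 5%.

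**The case against.** The strongest reply has four parts.

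**Counting from the study's own baseline is an explicit choice.** The SAP defines TEAEs that way, and prior and no-prior exposure are shown separately, so first-exposure onset can be read from the no-prior column. This stands, and the TEAE definition should not change. It does not answer the labelling: a drug-onset event still looks like pre-drug illness.

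**The subject is not lost from every discontinuation analysis.** A reader might infer that such events reach no AE-discontinuation output. The documents do not support that. Disposition reasons and the Kaplan-Meier analysis use the disposition CRF, and an investigator who gives an AE as the reason for stopping may also enter an AE. What remains is a possible mismatch with the SOC and preferred-term tables.

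**A treatment-dependent recording rule is not workable.** A reader might want 13.1 rewritten so that only conditions from before the first ALKS 5461 dose count as history. Protocol 9.4 keeps sites, investigators and the sponsor blinded to assignment in the applicable antecedent studies. Sites enrolling from 206 and 207 could not apply such a rule at Visit 2. This objection stands in full.

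**The antecedent studies have their own AE data.** A reader might infer that these events vanish from the safety evidence as a whole. That is not shown, because those studies' reports are not among the documents. Their reports could hardly show persistence through 208, however, so a gap in the 208 report remains.

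It is also fair that Continuing Subjects had to complete antecedent treatment. The prior-exposure column is already a selected, tolerating group, and no change to AE presentation removes that.

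**Conclusion.** The point holds in a limited form. For actively treated Continuing Subjects, an event (mainly a symptom) that began on ALKS 5461 and is ongoing and unchanged in 208 reaches no TEAE, PDEAE, AESI or TEAE-duration table and stands unmarked in the medical-history summary. If it leads to stopping, the disposition count and the SOC and preferred-term tables may not agree. This follows from the stated rules and needs no numerical assumption, except that sites record as 13.1 directs.

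No count or percentage of affected subjects can be defended. The documents give neither the number of actively treated rollovers nor the share with AEs ongoing at Visit 2, and any figure based on events unresolved at entry would also have to deduct those that later worsen, since they return to the AE form. For a given term, the shortfall in the prior-exposure column equals the share who carry it unchanged. This is a gap in the presentation of a long-term safety study. It should be closed, and it does not invalidate the planned TEAE tables.

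**What to change.** Leave Protocol 13.1 and the TEAE definition as they are. Add the following to the SAP, to be applied after the antecedent studies are unblinded:

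1. Link the antecedent AE data, and flag each AE with onset on or after the first ALKS 5461 dose that is ongoing at Visit 2.
2. Add one table of flagged events for the prior-exposure group, by preferred term, severity and relationship, with outcome where the records give it.
3. Include flagged events in the AESI listings.
4. In the medical-history table, show them apart from conditions that preceded the drug.
5. Reconcile AE discontinuations on the disposition CRF with AE records, so that a flagged event that led to stopping appears in the discontinuation tables by SOC and preferred term.

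The extra data demand is small: SAP 3.1 already needs antecedent treatment identity for the exposure grouping, and SAP 3.2.1 already needs antecedent data for the efficacy baseline. The cost is one merge, one table and a slightly less favourable prior-exposure column.
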